5.4.1 Efficacy Analyses According to immune-related RECIST (irRECIST)

Tumor assessments and overall response to the treatment according to irRECIST are presented in Section 13.2. The confirmation of progressive disease (irPD) is required at least 4 weeks after the initial irPD. If irPD at two consecutive tumor assessment visits with less than 4 weeks, the additional confirmation of irPD visit is required. If irPD is confirmed, the documented start date of irPD is determined as follows:

1. The date of the initial irPD if it is confirmed on consecutive tumor assessment visits.
2. The date of the second irPD if the initial irPD is confirmed not on consecutive tumor assessment visits.

The best overall response (BOR) is defined as follows:

- **irCR**

To achieve BOR of irCR, irCR must be observed at two consecutive tumor assessment visits with at least 4 weeks apart before the confirmed irPD, death, or end of study (whichever occurs first). If complete response at two consecutive tumor assessment visits with less than 4 weeks, the confirmation of irCR at the next assessment visit is required. The documented start date of irCR is defined as the date of the initial irCR.

- **irPR**

When BOR of irCR is not achieved, BOR of irPR can be achieved by that an initial irPR is confirmed by irPR or irCR at next consecutive visit (≥ 4 weeks after the first irPR response). If irPR or irCR happens at two consecutive tumor assessment visits within 4 weeks, the additional confirmation of irPR (irPR or irCR in a later visit) is needed for BOR of irPR. The documented start date of irPR is the date of the initial irPR.

- **irSD**

If the documented start date of irPD is not the first evaluable tumor assessment visit after the first dose of study drug and the BOR is not a confirmed irCR/irPR, then the BOR is stable disease (irSD) when the duration of irSD is no less than 5 weeks. The duration of irSD is defined as the time from the first dose date to the documented start date of irPD, death, or the last evaluable tumor assessment (whichever occurs first).

- **irPD**

If the documented start date of irPD is the first evaluable tumor assessment visit after the first dose of study drug, then the BOR is irPD.

Table 1 listed general rules in the derivation of BOR with two consecutive tumor response results.

Table 1 Derivation of BOR with Two Consecutive Tumor Response Results

| Timepoint 1 Initial Response | Timepoint 2 Follow-up Response ≥ 4 weeks | BOR |
|---------------------------------|--|--|
| irCR | irCR | irCR |
| irCR | irPR/irSD/irPD | irSD/irPR* |
| irPR | irPR/irCR | irPR |
| irPR | irSD | irSD |
| irPR | irPD | irSD |
| irSD | irSD | irSD |
| irSD | irPD | irSD, provided minimum irSD duration met |
| irPD | irPD | irPD |

*If an irCR is truly met at first time point, then any disease seen at a subsequent time point, even disease meeting irPR criteria relative to baseline, makes the disease irPD at that point (since disease must have reappeared after irCR). Best response would be irSD. However, sometimes 'irCR' may be claimed when subsequent scans suggest small lesions were likely still present and in fact the patient had irPR, not irCR at the first time point. Under these circumstances, the original irCR should be changed to irPR and the best response is irPR.

- **irNE**

The BOR will be irNE in the following scenarios:

- No evaluable tumor assessment
- Only one evaluable tumor assessment with the result of either irPD or irCR/irPR/irSD but the duration of irSD is less than 5 weeks.

- **Handling of Missing /Not Evaluable Tumor Assessments**

The following rules will be used to handle missing and/or not evaluable tumor assessments:

- One missing or not evaluable tumor assessment will be ignored if it is between two evaluable tumor assessments.
- All the missing and/or not evaluable tumor assessments will be ignored if they are the only ones in between two irPDs. In this case, the irPD is confirmed and the documented start date of irPD is the date of the first irPD.
- All the missing and/or not evaluable tumor assessments will be ignored if there is no evaluable tumor assessment after them.
- Two irCRs, two irPR, or irPR and irCR with two or more missing and/or not evaluable tumor assessments in between will result in not evaluable result, i.e., irNE.

Objective Response Rate (ORR)

The objective response rate (ORR) is the proportion of patients achieving a best overall response of confirmed irPR or irCR according to irRECIST from first dose date until disease progression, death, or end of study (whichever occurs first). Subjects who do not have a tumor response assessment for any reason will be considered nonresponders and will be included in the denominator when calculating the response rate. The count and percentage for the ORR will be summarized by dose group.

Time to Response (TTR)

The time to response (TTR) is defined as the elapsed time (weeks) from the first dose date to the documented start date of confirmed irCR/irPR according to irRECIST. The descriptive statistics for the TTR will be summarized by dose group for the patients with the BOR of confirmed irCR/irPR.

Duration of Response (DOR)

The duration of response (DOR) is defined as the time (months) from the documented start date of confirmed irCR/irPR according to irRECIST until the documented start date of irPD or death (whichever occurs first).

For subjects with the BOR of irCR/irPR who did not die and had no documented progression before the cut-off date for the end of the study, or before early discontinuation (including discontinuations due to toxicity, undocumented clinical progression, change of cancer treatment, or decreasing performance status), and who died or progressed after more than one missed visit, will be censored on the date of their last assessment with the BOR of irCR, irPR or irSD.

The descriptive statistics (median and its standard error, Q1 and Q3) for the DOR will be summarized by dose group for the patients with the BOR of confirmed irCR/irPR using Kaplan-Meier method.

Progression-Free Survival (PFS)

Progression-free survival is defined as alive without confirmed irPD using irRECIST at the end of study or certain evaluation time points such as 3 months, 6 months, etc. The time for PFS is defined as the elapsed time from first dose date to the documented start date of irPD or death (whichever occurs first).

In analysis of PFS, the censoring rule is as follows:

- Subjects who did not die and had no documented progression (confirmed irPD) before the cut-off date for the end of the study, or before early discontinuation (including discontinuations due to toxicity, undocumented clinical progression, change of cancer treatment, or decreasing performance status), PFS will be censored on the date of their last evaluable assessment.
- Subjects who died or progressed after more than one missed visit, or non-evaluable assessment, or a combination of two, PFS will be censored on the date of their last evaluable assessment before the death or progression.

The rate for PFS will be summarized by evaluation time point and dose group. The time curve and median of PFS will be estimated and reported by the Kaplan-Meier method.

Disease Control Rate (DCR)

The disease control rate (DCR) is the proportion of patients achieving the BOR of confirmed irCR, confirmed irPR or irSD with the duration of at least 5 weeks. The count and percentage for the DCR will be summarized by dose group.

Clinical Benefit Rate (CBR)

The Clinical benefit rate (CBR) is the proportion of patients achieving the BOR of confirmed irCR, confirmed irPR or durable irSD (i.e., the duration of at least 24 weeks). The count and percentage for the CBR will be summarized by dose group.

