- r. Tumor assessments will be performed based on irRECIST and RECIST1.1. Treatment decisions will be based on irRECIST. Tumor assessments will be carried out during the Pretreatment Phase and then every 6 weeks (during the 6th week; counting from C1D1) during treatment cycles in both the Treatment Phase and the Extension Phase. CT scans (with oral and intravenous contrast) of chest, abdomen, and pelvis and of other known sites of disease will be obtained at Screening (within 28 days prior to Cycle 1/ Day 1), using the above tumor assessment schedule, and as indicated clinically. Skin lesions may only be considered as non-index lesions (no photographs required) or as new lesions to add to the tumor burden sum. Subjects with SCCHN must also have head and neck scans performed at all tumor assessment timepoints. MRI scans may be used instead of CT scans for (head, neck) abdomen and pelvis; however, chest must be assessed using CT. Chest disease may not be followed using chest x-ray. CT scans should be performed with oral and iodinated IV contrast and MRI scans with IV gadolinium chelate unless there is a medical contraindication to contrast. If iodinated IV contrast is contraindicated, chest CT should be performed without IV contrast. The same method of assessment must be used at all time points as used at Screening.
- s. Screening brain scans will be performed by MRI pre- and post- gadolinium or CT with contrast within 4 weeks prior to C1D1. During the Treatment Phase, CT/MRI of the brain will be performed if clinically indicated, and within a target of 1 week after a subject achieves a irCR. For subjects with history of treated brain metastases, brain scans will be performed at every tumor assessment time point. The same methodology and scan acquisition techniques used at screening should be used throughout the study to ensure comparability.

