| Definition of New lesion | Any lesion which was not recorded at baseline. There is no minimum size criteria to identify a new lesion and clinical judgment must be used by the PI 
 • May include a lesion in an anatomical location that was not scanned at baseline (i.e. brain) • Should be unequivocal and not due to differences in scanning technique • If equivocal, should be assessed at next timepoint; if present, PD is the date the lesion was first seen (not the date confirmed) | | | | | | | | | | | | | | |
|---|--|---|--|-----------------------|---------------------|--|---------|-----------|---------|-----------|---|--|---|--|-----------------------|
| 3. irRECIST Overall Tumor Assessment | | | | | | | | | | | | | | | |
| irCR | 
 • Complete disappearance of all measurable and nonmeasurable lesions (from baseline) and there are no unequivocal new lesions (unconfirmed irCR). • Lymph nodes must decrease to < 10 mm in short axis. • Confirmation of response is required ≥ 4 weeks later, preferably at next timepoint, to be considered a confirmed irCR. | | | | | | | | | | | | | | |
| irPR | 
 • If the SOD_{timepoint} of TLs decreases by $\geq 30\%$ compared to SOD_{baseline} and there are no unequivocal new lesions, and no progression of non-target disease, it is an irPR (unconfirmed). • Confirmation is required ≥ 4 weeks later, preferably at next timepoint, to be considered a confirmed irPR. | | | | | | | | | | | | | | |
| irSD | 
Failure to meet criteria for irCR or irPR in the absence of irPD.
 
 • If the sum of the TLs and the status of the non-target lesions do not reach the criteria to meet irPR or irPD (increase $\geq 20\%$ and at least 5 mm absolute increase in SOD compared to nadir[†]) the response is irSD. • irSD = neither 30% decrease compared to SOD_{baseline} or 20% increase and at least 5 mm absolute change compared to nadir. • [†]SOD_{nadir}: Lowest measure SOD of TLs at any timepoint from baseline onward. | | | | | | | | | | | | | | |

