| irPD | 
Minimum 20% increase and a minimum 5 mm absolute increase in SOD compared to nadir, or irPD for non-target lesion(s) or unequivocal new lesion(s).
 
 • Confirmation of progression is recommended at a minimum of 4 weeks after the first irPD assessment (preferably at next tumor assessment timepoint). 
The decision to continue study treatment after the first evidence of PD is at the Investigator's discretion based on the clinical status of the subject as described in table below.
 
  
 	Clinically Stable	Clinically Unstable	
 
 Imaging	Treatment	Imaging	Treatment	
   
 1st radiologic evidence of PD	Repeat imaging at ≥ 4 weeks (next TA timepoint) to confirm PD	May continue study treatment at the Investigator's discretion while awaiting confirmatory scans	Repeat imaging at ≥ 4 weeks to confirm PD per physician discretion only	Discontinue treatment	
  
 | | Clinically Stable | | Clinically Unstable | | Imaging | Treatment | Imaging | Treatment | 1 st radiologic evidence of PD | Repeat imaging at ≥ 4 weeks (next TA timepoint) to confirm PD | May continue study treatment at the Investigator's discretion while awaiting confirmatory scans | Repeat imaging at ≥ 4 weeks to confirm PD per physician discretion only | Discontinue treatment |
| | Clinically Stable | | Clinically Unstable | | | | | | | | | | | | |
| | Imaging | Treatment | Imaging | Treatment | | | | | | | | | | | |
| 1 st radiologic evidence of PD | Repeat imaging at ≥ 4 weeks (next TA timepoint) to confirm PD | May continue study treatment at the Investigator's discretion while awaiting confirmatory scans | Repeat imaging at ≥ 4 weeks to confirm PD per physician discretion only | Discontinue treatment | | | | | | | | | | | |

| | | | | | |
|---|--|--|---|--|--|
| | Subsequent scan confirms PD | No additional imaging required | Discontinue treatment | No additional imaging required | N/A |
| | Subsequent scan shows SD, PR or CR | Continue regularly scheduled imaging assessments | Continue study treatment at the Investigator's discretion | Continue regularly scheduled imaging assessments | May restart study treatment if condition has improved and/or clinically stable per Investigator's discretion |

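### The SAP has two dating rules for progression by a new lesion first called equivocal: 5.4.1 gives a PFS about one scan (6 weeks) longer than the irRECIST table, and DCR changes if the lesion is first seen at the first scan.

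*SAP*

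**What the plan says.** SAP 5.4.1 requires irPD to be confirmed at least 4 weeks later and then sets its documented start date by two rules. Rule 1 is "The date of the initial irPD if it is confirmed on consecutive tumor assessment visits". Rule 2 is "The date of the second irPD if the initial irPD is confirmed not on consecutive tumor assessment visits". Neither mentions a lesion first recorded as equivocal.

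That start date drives the other definitions in 5.4.1. It ends PFS, DOR and the duration of irSD, and it separates irPD from irSD as best overall response: a start date at the first evaluable post-dose scan makes the BOR irPD, and a later one leaves irSD open. Table 1 of 5.4.1 classes irSD followed by irPD as irSD if the minimum duration is met. DCR counts irSD of at least 5 weeks, and CBR counts irSD of at least 24 weeks.

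The irRECIST table in SAP 13.2 (Table 4, new-lesion entry) says: "If equivocal, should be assessed at next timepoint; if present, PD is the date the lesion was first seen (not the date confirmed". Protocol Appendix 1 carries the same rule. Elsewhere in that table a new lesion makes a visit irPD only if it is unequivocal.

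Section 5.4.1 does point to the table: "Tumor assessments and overall response to the treatment according to irRECIST are presented in Section 13.2". It does not say which date governs. Scans are scheduled "every 6 weeks (during the 6th week; counting from C1D1").

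**The concern.** A scan that shows only an equivocal new lesion is not irPD under the table, so it is scored on its other findings, for instance irSD. If the lesion is present at the next scan, that later scan is the first one scored irPD. Section 5.4.1 then starts progression at the later scan, while 13.2 starts it at the earlier one. Two programmers working from the same SAP could derive different PFS times and, in some records, a different best response.

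The literal reading of 5.4.1 always gives the more favourable answer: longer PFS and, in some records, an extra subject with disease control. Efficacy is summarised by dose group, with 6 subjects planned per escalation cohort, so a single reclassified subject is visible. Clinical benefit is also one of the inputs to choosing the RP2D (protocol 9.1.1.4).

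**Working it through.** The plan has no figure to reproduce here. The check applies both dating rules to the same scan records.

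**Inputs.** Scan interval 6 weeks (SAP 13.1, footnote r). Confirmation at least 4 weeks later, and minimum irSD duration 5 weeks (SAP 5.4.1). Durable irSD 24 weeks (SAP 5.4.1, CBR). Cohort size 6, expansion 6 to 16, maximum total 40 (SAP 4).

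**Record.** Target lesions are stable and a new lesion is equivocal at one scan (scored irSD). The next scan is scored irPD, and irPD is confirmed 6 weeks after that, consecutively, so rule 1 applies. Weeks are nominal. Each pair reads 5.4.1 taken literally / 13.2 first-seen date.

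| First seen | Scored irPD | irPD start (= PFS, weeks) | BOR | In DCR | In CBR |
|---|---|---|---|---|---|
| Week 6 | Week 12 | 12 / 6 | irSD / irPD | yes / no | no / no |
| Week 12 | Week 18 | 18 / 12 | irSD / irSD | yes / yes | no / no |
| Week 18 | Week 24 | 24 / 18 | irSD / irSD | yes / yes | yes / no |
| Week 24 | Week 30 | 30 / 24 | irSD / irSD | yes / yes | yes / yes |

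**PFS.** The difference is 6 weeks in every row, or 6 × 7 / 30.4375 = 1.4 months. In the first row PFS doubles. Under rule 2 the gap can exceed one interval, because the SAP date moves to the second irPD.

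**DCR.** Only the first row changes, because only there does the first-seen date fall on the first evaluable scan. One such subject is 100/6 = 16.7 points in a cohort of 6, 100/16 = 6.3 points in 16 and 100/40 = 2.5 points in 40, if all are in the denominator.

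**CBR.** On nominal weeks the change occurs when the lesion is first seen at Week 18. A scan during week k falls 7(k − 1) to 7k − 1 days after Day 1, so a Week 24 scan falls at 161 to 167 days, or 23.0 to 23.9 weeks, just short of 24. On actual dates the change therefore moves to a lesion first seen at Week 24: 29.0 to 29.9 weeks under 5.4.1, against 23.0 to 23.9 under 13.2.

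**Landmark PFS.** SAP 5.4.1 names 3 and 6 months as example time points. Three months is 3 × 30.4375 / 7 = 13.0 weeks. A lesion first seen at Week 12 and scored irPD at Week 18 is progression-free at that point under 5.4.1 only. Six months is 26.1 weeks, and the Week 24/Week 30 record splits in the same way.

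**The case against.** The strongest reply is that there is no conflict, because 5.4.1 refers to 13.2. On this layered reading, 13.2 decides which visit is progression and 5.4.1 then deals with confirmation. Once the lesion persists, the first sighting becomes the initial irPD, and rule 1 returns Week 6 with BOR irPD. This reading is possible, but no sentence states it. The table never says the earlier scan is re-scored, and Table 1 sends irSD then irPD to irSD. Where the SAP does intend re-scoring it says so: the Table 1 footnote explains when an irCR is changed to irPR. Nothing comparable exists for equivocal lesions.

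A second reply is that the case is narrow and the endpoints are secondary and descriptive. That stands. The documents give no rate for this pattern of progression, so a count of affected subjects cannot be derived from them. SAP 9 also places derivation rules in separate documents, and the CRF is not available here, so an equivocal flag may already exist. A programming specification would still have to choose between two rules in the SAP.

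A reader might infer something stronger for a subject whose scanning stops at Week 12: that 5.4.1 censors PFS at Week 12 while 13.2 gives an event at Week 6. The documents do not establish this. The new-lesion rule supplies a date but does not waive confirmation. Section 5.4.1 requires confirmation, whereas the irPD entry in 13.2 only recommends it. Whether the Week 12 sighting is the initial irPD or its confirmation is unstated.

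**Conclusion.** The point holds as two stated rules that give different progression dates for the same record, with no order of precedence. For a subject whose progression is a new lesion first called equivocal and present at the next scan, literal use of 5.4.1 adds about 6 weeks of PFS. BOR and DCR change only if the equivocal scan is the first evaluable one. Later first sightings can shift CBR or a landmark PFS rate but not DCR.

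This rests on three assumptions: the equivocal scan stays scored irSD, irPD is later confirmed on consecutive visits, and the full cohort is in the denominator. Because the SAP runs efficacy on the Response Evaluable Set, a smaller denominator would make one subject weigh more than 17 points.

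Three larger inferences are not supported. The two-scan event-versus-censoring difference depends on the unsettled confirmation question. No number of affected subjects follows from the documents. Not every affected subject moves into DCR. The primary endpoints are not touched directly, since clinical benefit enters RP2D selection only as one part of a joint judgement. The change is worth making because it is cheap and brings 5.4.1 into line with the criteria in the protocol.

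**What to change.** - Add to the start-date rules in SAP 5.4.1: when irPD rests on a new lesion recorded as equivocal at the preceding assessment, the documented start date of irPD is the date that lesion was first seen (Section 13.2).
- State that the earlier visit is re-scored irPD for BOR, DCR, CBR, DOR and PFS, and add a Table 1 footnote modelled on the existing irCR one. Without it, the amended text would return irPD for the Week 6/12/18 record while Table 1 still returned irSD, since the Week 6 scan already meets the 5-week minimum.
- State whether the scan showing persistence counts as the initial irPD or as its confirmation. This also settles event or censoring for a subject with no further scan.
- Check that the equivocal or unequivocal status of each new lesion is available in the tumour assessment data, and add a flag if it is not.

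The cost is a few sentences, one footnote and possibly one data item. No site procedure changes. The downside for the sponsor is that PFS and DCR become slightly less favourable.

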##### **Secondary Efficacy endpoints:**

- Objective response rate

The ORR is the proportion of subjects achieving a best overall response of confirmed partial or complete response (irPR + irCR), according to irRECIST ([Appendix 1](#)) from first dose date until disease progression/recurrence. Subjects who do not have a tumor response assessment for any reason will be considered nonresponders and will be included in the denominator when calculating the response rate.

- Duration of response

Duration of response is defined as the time from the date of first documented confirmed irCR/irPR until the first documentation of confirmed disease progression or death, whichever comes first.

- Progression-free survival

Progressive-free survival is defined as the time from first dose date to the date of the first documentation of confirmed disease progression or death (whichever occurs first) using irRECIST. The censoring rule for events will be defined in the SAP.

- Disease control rate

The DCR is the proportion of subjects achieving irPR + irCR + irSD from first dose date until disease progression/recurrence.

- Clinical benefit rate

The CBR is the proportion of subjects achieving irPR + irCR + irSD [lasting at least 24 weeks] from first dose date until disease progression/recurrence.

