| Subjects may continue receiving study treatment while waiting for confirmation of irPD if they are clinically stable as defined by the following criteria: | | | | | |
| 
 • Absence of signs and symptoms (including worsening of laboratory values) indicating disease progression • No decline in ECOG performance status • Absence of rapid progression of disease • Absence of progressive tumor at critical anatomical sites (e.g., cord compression) requiring urgent alternative medical intervention | | | | | |
| If irPD is confirmed and the subject is experiencing extraordinary clinical benefit, site must contact Sponsor to discuss continuing treatment | | | | | |
| irNE | Used in exceptional cases where insufficient data exists due to poor quality of scans or missed scans or procedure | | | | |

Derivation of irRECIST overall responses

| Measurable response | Nonmeasureable response | | |
|--------------------------------------|---------------------------|--------------------|--------------------------------|
| Target Lesions (% change in SOD)* | Non-Target Lesions Status | New Lesions Status | Overall Response (irRECIST) |
| ↓100 | Absent | Absent | irCR [¥] |
| ↓100 | Present/NE | Absent | irPR [¥] |
| ↓≥30 | Present/Absent/NE | Absent | irPR [¥] |
| ↓<30 to <20↑ | Present/Absent/NE | Absent | irSD |
| ↓100 ↓≥30 ↓<30 to <20↑ NE | Present/Absent/NE | Present | irPD [¥] |
| ↓100 | Unequivocal | Any | irPD [¥] |

| | | | |
|----------------------------|-------------------|--------|-------------------|
| ↓≥30 ↓<30 to <20↑ NE | progression | | |
| ↑≥20 from nadir | Any | Any | irPD [¥] |
| NE | Present/Absent/NE | Absent | irNE [¥] |

* Decreases assessed relative to baseline, including measureable lesions only.

[¥] Assuming response (irCR) and progression (irPD) are confirmed by a second, consecutive assessment at least 4 wk apart.

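### SAP 5.4.1 rule 2 counts two non-consecutive irPDs as confirmed progression, against the consecutive-assessment footnote in SAP 13.2 and protocol Appendix 1, and so creates PFS and DOR events that the footnote rule would not

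*SAP*

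**What the plan says.** SAP 5.4.1 begins its irPD rules with an interval: "The confirmation of progressive disease (irPD) is required at least 4 weeks after the initial irPD". It adds that irPDs at two consecutive visits less than 4 weeks apart need a further confirming visit. Two dating rules follow. Rule 1 is "The date of the initial irPD if it is confirmed on consecutive tumor assessment visits". Rule 2 is "The date of the second irPD if the initial irPD is confirmed not on consecutive tumor assessment visits".

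Later in 5.4.1, gaps in imaging get their own rule: "All the missing and/or not evaluable tumor assessments will be ignored if they are the only ones in between two irPDs". In that case irPD is confirmed and dated at the first irPD.

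The footnote to the response-derivation table in SAP 13.2, repeated in protocol Appendix 1, reads: "Assuming response (irCR) and progression (irPD) are confirmed by a second, consecutive assessment at least 4 wk apart". The irPD row of the same appendix is softer: "Confirmation of progression is recommended at a minimum of 4 weeks after the first irPD assessment (preferably at next tumor assessment timepoint").

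Protocol 9.7.1.1 measures PFS from first dose "to the date of the first documentation of confirmed disease progression or death (whichever occurs first) using irRECIST", and for PFS it leaves only the censoring rule to the SAP. In SAP 5.4.1 both PFS and DOR end at the documented start date of irPD or at death. SAP section 7 declares no changes to the planned analysis.

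**The concern.** Section 5.4.1 refers the reader to 13.2 for irRECIST and then departs from the footnote there. Two programmers, one working from each section, would derive different PFS, DOR and ORR from the same scans.

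The subjects affected are those whose first irPD cleared, which is the group that confirmation of irPD is meant to protect. Protocol 9.5.2 and its Table 3 allow them to stay on treatment and on regular imaging, so the pattern can occur. Under rule 2, once such a subject has had one cleared irPD, the next single irPD is a progression event.

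The rule is also asymmetric. In SAP Table 1 an irPR followed by irSD is not a confirmed response, yet irPD, irSD, irPD is confirmed progression.

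These endpoints are secondary, but evidence of clinical activity is one of the guidelines for choosing the RP2D (protocol 9.1.1.4).

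**Working it through.** The plan gives no figure on this point to reproduce. The check is to establish what rule 2 covers and then trace both rules through scan sequences.

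**What rule 2 covers.** Two irPDs can fail to be on consecutive visits in two obvious ways.
- The scans between them are missing or not evaluable. SAP 5.4.1 handles this separately and dates it at the first irPD, so it is not rule 2.
- An evaluable scan between them is not irPD. This is what remains. SAP 13.2 defines irSD as "Failure to meet criteria for irCR or irPR in the absence of irPD", so an intervening irSD means that the first irPD was not confirmed at the next assessment.

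**Traces.** Scans are every 6 weeks from week 6 (protocol 9.5.2) and all evaluable; P = irPD, S = irSD, R = irPR. Without a confirmed irPD, PFS is censored at the last evaluable scan (SAP 5.4.1).

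| Sequence | SAP 5.4.1 rule 2 | Consecutive confirmation |
|---|---|---|
| P-S-P-P | event, week 18 | event, week 18 |
| P-S-P | event, week 18 | censored, week 18 |
| P-S-P-S-S | event, week 18 | censored, week 30 |
| P-S-S-P-S | event, week 24 | censored, week 30 |
| P-S-P-S-P-P | event, week 18 | event, week 30 |
| P-S-P-R-R | event, week 18; irPR falls after the ORR window | irPR from week 24; censored, week 30 |
| P-R-R-P-R-R | event, week 24; DOR 24 − 12 = 12 weeks, event | censored, week 36; DOR 36 − 12 = 24 weeks, censored |

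**All six-scan sequences.** There are 3^6 = 729. Let the second irPD fall at scan j (3 to 6), with the first not adjacent to it. The first can take j − 2 positions, the other j − 2 scans before j are each S or R, and the 6 − j scans after j are free. The count is (j − 2) × 2^(j−2) × 3^(6−j).
- j = 3, 4, 5, 6: 54 + 72 + 72 + 64 = **262** sequences trigger rule 2.
- Later irPD confirmed at the next scan, so PFS is identical: 18 + 24 + 24 = **66**.
- Later irPD is the last scan, so same PFS date but event instead of censored: **64**.
- PFS ends earlier under rule 2: 262 − 66 − 64 = **132**. Of these, 128 are set against a later censoring and 4 against a later event.
- PFS later under rule 2: **0**.

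With the ORR window closed at the irPD date, a confirmed irPR is lost in 15 sequences and gained in none.

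**Response window.** The requirement that response come before confirmed irPD is written only in the irCR bullet. The irPR bullet has no such limit. In P-S-P-R-R the literal BOR is therefore still irPR, and so are DCR and CBR, which are built on BOR. The response is lost from ORR because the ORR definition counts response only up to progression.

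**The case against.** **The appendix is not uniformly strict.** The irPD row recommends confirmation and prefers the next time point; protocol 9.5.2 likewise says the repeat scan is generally the next scheduled one. A reader might infer that the appendix everywhere demands a consecutive scan, but the direct conflict is only with the footnote. This stands. Still, the softer wording concerns whether and when the confirming scan is done. It does not say that an irPD which has cleared can confirm a later one.

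**The scope of rule 2 is inferred.** The sentence before the two rules deals with consecutive irPDs less than 4 weeks apart. With irPD at weeks 6, 8 (unscheduled) and 12, the week-6 irPD is confirmed at week 12, which is not the visit next to week 6, and the second irPD would be week 8. This fits poorly, because the SAP calls such visits consecutive and every visit in the run shows irPD. The text does not exclude it, though, so a replacement must cover this case.

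**A reader might infer that rule 2 always shortens PFS, or that P-S-P-R-R turns BOR into irSD.** Neither is supported. The PFS date is unchanged in 66 + 64 = 130 of the 262 sequences, and the irPR bullet leaves BOR as irPR.

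**The stakes are limited.** The endpoints are descriptive and secondary in a Phase 1 study, and modified RECIST 1.1, which needs no PD confirmation, is reported alongside. This stands, and it limits the point's weight; it does not settle which irRECIST rule applies.

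**Conclusion.** The conflict is real: it lies inside the SAP (5.4.1 against the 13.2 footnote) and between SAP 5.4.1 and protocol Appendix 1. Its effect is confined to subjects with an irPD, an evaluable non-irPD scan, and a later irPD that is not itself confirmed. For them rule 2 records a PFS event where the footnote rule gives censoring, on the same date if that irPD is the last scan and at a later date if scans follow, or occasionally a later event. It can shorten DOR in the same way. It closes the response window for irCR and for ORR, but not clearly for a BOR of irPR. In the enumeration PFS is never longer under rule 2.

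The size in patients is unknown, because the documents give no frequency for such patterns and the counts weight every sequence equally. One lost responder is 1/6 = 16.7 percentage points of ORR if all six subjects of a cohort are in the denominator; a reader should not take that as an expected bias.

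The traces assume 6-weekly evaluable scans, no deaths and no new anticancer therapy. The conclusion also rests on reading rule 2 as covering an intervening evaluable non-irPD scan. This should be corrected, but it does not touch the primary endpoints.

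**What to change.** Replace rule 2 in SAP 5.4.1 with text to this effect:

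> An irPD followed by an evaluable assessment that is not irPD is not confirmed. A later irPD is a new initial irPD, needs its own confirmation at the next consecutive evaluable assessment at least 4 weeks later, and takes its own date. If consecutive irPDs are less than 4 weeks apart and a later consecutive irPD at least 4 weeks after the first confirms it, the date is that of the first irPD. A final irPD with no later evaluable scan is unconfirmed and is censored at that scan, with a sensitivity analysis that counts it as an event.

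For DOR, also state the censoring date in that last case: the present DOR text appears to point to the last assessment showing irCR, irPR or irSD, which would precede the final irPD. Say in the irPR bullet whether confirmed irPD closes the window, so that BOR and ORR agree. The change concerns endpoint derivation only, not treatment decisions.

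If the sponsor does intend rule 2, it should give the reason, amend the 13.2 footnote and list the departure from protocol Appendix 1 in SAP section 7.

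The cost is SAP wording and derivation code. The statistical downside is that most affected subjects move from event to censored: in the enumeration 64 + 128 = 192 of the 196 changed sequences, against 4 that become later events. That censoring may be informative if scanning stopped because the subject was deteriorating, hence the sensitivity analysis.
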